- **Screen Only group:** Patients will receive screening for AD (n=600). Patient and family members will receive a letter about how the patient performed on the screening. If they screen positive (e.g. ≤5 on the MIS-T or clock draw pass/fail with the MIS-T) the patient and family member will receive an infographic and some information about local clinical resources for them to peruse regarding follow-up care. The patient's PCP will also be notified of the screening results. Additionally, at the 24 month follow up, family members will be asked to complete the IQCODE to detect possible cognitive impairment in the participant
- **Screen Plus group:** Patients will receive screening for AD (n=600). Patient and family members will receive a letter about how the patient performed on the screening. If they screen positive (e.g. ≤5 on the MIS-T and clock draw pass/fail with the MIS-T), the patient and family member will receive an infographic. Also, the family member will receive two follow-up phone calls. One from the COADS Study PI (or their designee) and one from a staff member at the Aging Brain Care Program (ABC). This phone call will include an opportunity for the family to ask questions and have a conversation about the program and diagnostic evaluation and management. Follow-up diagnostic evaluation can occur at the Aging Brain Care Program or, if preferred in the patient's home with trained personnel in an attempt to replicate the clinic visit. Dyads will be offered transportation assistance if they chose the Aging Brain Care Program and are unable to get themselves there. If the visit occurs in the home, dyads will also be given the opportunity to have a post home visit meeting which can occur in the Aging Brain Care Program or at home. Dyads have the option to refuse the follow-up visit. The patient's PCP will also be notified of the screening results. Additionally, at the 24 month follow up, family members will be asked to complete the IQCODE to detect possible cognitive impairment in the participant
- **Control group:** Patients will receive no AD screening (n=600 dyads) at baseline. At the 24-month follow-up, patients will complete the Cognitive Change Index (CCI) and an interview with the family member will be completed to detect possible cognitive impairment.

Participants

- Patients will be adults 65 years or older;

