Secondary outcomes	Family member Mood	Depressive symptoms	The Patient Health Questionnaire -9 (PHQ-9)	9-item measures of depressive symptoms.	Depression Severity: 0-4 none, 5-9 mild, 10-14 moderate, 15-19 moderately severe, 20-27 severe.	B 6 12 18 24	Family reported Patient reported
		Anxiety	Generalized Anxiety Disorder Scale-7 (GAD-7)	7-item measure of anxiety	GAD-7 total score for the seven items ranges from 0 to 21. Scores of 5, 10, and 15 represent cut points for mild, moderate, and severe anxiety.	B 6 12 18 24	Family reported Patient reported
	Caregiver preparedness	Caregiver preparedness	Caregiver Preparedness Scale	8-item measure with 1 open-ended question. Self-rated instrument that consists of eight items that asks caregivers how well prepared they believe they are for multiple domains of caregiving. Responses are rated on a 5-point scale with scores ranging from 0 (not at all prepared) to 4 (very well prepared).	The scale is scored by calculating the mean of all items answered with a score range of 0 to 4. The higher the score the more prepared the caregiver feels for caregiving	B 6 12 18 24	Family reported
	Caregiving self-efficacy	Caregiving self-efficacy	The Revised Scale for Caregiver Self Efficacy	15 item measure with three domains of caregiving self-efficacy: Obtaining	Use of a total score reflecting the sum of all 15 items is contrary to	B 6 12 18 24	Family reported

				Respite, Responding to Disruptive Patient Behaviors, and Controlling Upsetting Thoughts	the view of self-efficacy as domain specific and can mask significant relationships between subscales and other constructs. For these reasons, we strongly advocate using scores for the three subscales rather than a total score.		
Other measures	Socio-demographics	Socio-demographics	COADS Created	Questionnaire to measure items such as relationship to the patient/family, frequency and type of contact with the patient, geographic distance from the patient, education level, annual income, self-reported health status, etc.	Co-variates	B	Family reported Patient reported
	Cognitive impairment	Cognitive impairment	Mini-Cog	For in-person recruitment we will use the Mini-Cog which is a 3 minute test of cognition including a clock draw and 3 word recall	Score ranges from 0-5. 0=impaired; 1-2 abnormal clock draw then positive for cognitive impairment; 1-2 Normal clock draw then negative for cognitive impairment; 3 negative screen	B (patients randomized to screening only)	Patient reported

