			MIS-T	The MIS-T is comprised of four-items with semantic cues to assess episodic memory performance; a cut-point of 5 or less was used to classify those with potential memory impairment	6+ not impaired <=5 impaired	B (patients randomized to screening only)	Patient reported

			Cognitive Change Index (CCI-20-s)	The Cognitive Change Index (CCI) is a tool used to assess the perception of cognitive decline in memory, executive function, and language domains from both self and informant perspectives.		24 month	Patient Reported
			IQ CODE	16-item measure of the patient's changes in cognition and function as reported by the family	Sum each question and divide by the number of questions (16). The result is a score that ranges from 1 to 5. An average score of 3 means that the subject is rated as 'no change'. A score of 4 means 'a bit worse', and a score of 5 is 'much worse'.	24 months	Family reported
		Knowledge of patient being screened for AD	COADS Created	2-items to assess if family members are aware if the patient has been screened in the study and about their performance	Yes or no	6 12 18 24	Family reported
		Evidence of screening for AD or new diagnoses of AD	COADS Created	EHR diagnosis	Yes or no	B 6 12 18 24	EHR
		Caregiver burden	Oberst Caregiving Burden Scale	15-item questionnaire that rates 15 different types of caregiving tasks based on perceived time and difficulty (Each item is scored on a 5-point response scale.		B 12 24	Family reported
		COADS Loneliness Assessment for patient and caregiver	PROMIS NIH Toolbox Loneliness (Ages 18+)-Fixed Form	5-item questionnaire to assess loneliness on a scale from 1-5		B 6 12 18 24	Family reported
		COADS COVID	NIH Toolbox	11-items to assess COVID-19		B 6	Patient reported

				impact and experience (Asked after the PHQ-9 and GAD-7)		12 18 24	
		Economic Impact ?	Health Motivation Scale	8-item questionnaire to assess health motivation	All response are on a 7 point Likert Scale of (7) strongly agree, (1) strongly disagree	24	Family reported
		Economic Impact?	Motivation to Change Lifestyle and Health Behaviors for Dementia Risk Reduction (MCLHB-DRR) Scale	11-item assessment with 5 section about perceived benefits, cues to action, general health motivation and self-efficacy	All response are on a 5 point Likert Scale of (5) strongly agree, (1) strongly disagree	24	Family reported
		Economic Impact	Resource Utilization in Dementia (RUD) Instrument			24	Family reported

Intervention Description and Timing of Measures

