- **Screen Only:** at baseline, the study personnel will administer the mini cog or clock draw and MIS-T to the patient. During COVID 19 restrictions, we are able to use phone recruitment only, if the participant is able, we will administer the clock draw aspect of the Mini-Cog or the mini-cog in person if applicable to capture the executive and visual spatial aspects of this test.

Dyads will then receive a letter with information about the patient's AD screening results, provided in plain language. For patients who score ≥ 6 on the MIS-T and the clock draw as a pass/fail measure, the patient and family member will both receive a letter and infographic indicating the patient's screening outcome results do not indicate signs of cognitive impairment. In cases where the patient scored ≤ 5 on the MIS-T and pass/fail on the clock draw or positive mini-cog screen, the patient and family member will both receive a letter indicating the patient scored lower than expected. The letter will encourage the patient and family member to discuss the results with the patient's PCP at the earliest possible time. The dyad will also receive a resource guide with local clinical sources with memory specialists. At the 24 month assessment Informant Questionnaire on Cognitive Decline in the Elderly (IQCODE) will be administered to the family member. The patient's PCP is also notified of the screening results.

- **Screen Plus:** As described above, research assistants will screen patients with the MIS-T and pass/fail on the clock draw or the mini-cog if possible. Patients, who score ≥ 6 on the MIS-T and pass/fail on the clock draw or mini-cog if possible, will receive a letter and infographic. If the patient scores ≤ 5 on the MIS-T or ≤ 2 and a pass/fail on the clock draw or the mini-cog if possible, the phone call and letter to the dyad will indicate that they will be receiving a follow-up call from the ABC Program (letter includes ABC contact name who will be calling and phone information). At the 24 month assessment, the Informant Questionnaire on Cognitive Decline in the Elderly (IQCODE) will be administered to the family member. The patient's PCP is also notified of the screening results.
- **Control Group (No screen, surveillance group)** Patients will not be screened for cognitive function at baseline. Similar to the design of cancer screening trials, this group

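### The positive-screen rule for patients given the MIS-T with a clock draw contradicts itself between the two screening arms, and no section says how discordant results are classified

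*Combined protocol and SAP*

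**What the plan says.** The point concerns patients screened with the MIS-T plus a clock draw. Background and Study Aims adds the clock to telephone MIS-T screening, for patients able to do it, to cover functions the MIS-T misses. It gives no rule for combining the two results.

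- **Study Design, Screen Only:** "If they screen positive (e.g. ≤5 on the MIS-T or clock draw pass/fail with the MIS-T".
- **Study Design, Screen Plus:** "If they screen positive (e.g. ≤5 on the MIS-T and clock draw pass/fail with the MIS-T".
- **Step 2: Enrollment, Screen Only, positive:** "In cases where the patient scored ≤ 5 on the MIS-T and pass/fail on the clock draw or positive mini-cog screen".
- **Step 2, Screen Only, negative:** "For patients who score ≥ 6 on the MIS-T and the clock draw as a pass/fail measure".
- **Step 2, Screen Plus, positive:** "If the patient scores ≤ 5 on the MIS-T or ≤ 2 and a pass/fail on the clock draw".
- **Step 2, Screen Plus, negative:** "Patients, who score ≥ 6 on the MIS-T and pass/fail on the clock draw or mini-cog if possible".
- **Table 2, MIS-T:** "6+ not impaired <=5 impaired", with no mention of the clock.
- **Table 2, Mini-Cog:** "1-2 abnormal clock draw then positive for cognitive impairment; 1-2 Normal clock draw then negative for cognitive impairment; 3 negative screen". This combines a clock with word recall, but only within the Mini-Cog.

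A positive result in Screen Only brings a letter saying the patient did less well than expected and a guide to local memory services. In Screen Plus it brings two telephone calls to the family member and the offer of a diagnostic evaluation.

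**The concern.** The screening result triggers the intervention. Aim 4 compares what follows a positive screen in Screen Plus with what follows one in Screen Only, so the same scores must open either pathway. Randomisation balances the patients, but it does not balance a classification rule that itself differs by arm. If the rule did differ, the Aim 4 contrast would mix the effect of the follow-up pathway with the effect of telling more families in one arm that the screen was positive.

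The outcome list before Table 2 calls this comparison exploratory. The Statistical Plan places it under a Secondary Aim heading, and it has its own hypothesis and its own power statement. Hypotheses 1–3 compare the two screening arms combined with Control, so they do not rest on the contrast between the screening arms.

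**Working it through.** **Plan's own figure.** The documents give no figure for screen positivity. The only figure attached to the affected comparison is Aim 4 power, 83.4% at 0.28 SD. A 4-df group-by-time test over five visits, with 540 dyads per group, a linear effect reaching 0.28 SD, the stated correlation structure (0.2, 0.8) and an assumed two-sided alpha of 0.05, gives 83.6%. Enrolment also agrees: 540/(1 − 0.10) = 600. The power figure is not in dispute.

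**Step 1: classify each score pattern.** Here 'literal' means Study Design as printed, with 'pass/fail' read as 'failed'.

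| MIS-T | Clock | Screen Only, literal (*or*) | Screen Plus, literal (*and*) | Table 2 (MIS-T alone) |
|---|---|---|---|---|
| ≤5 | failed | positive | positive | positive |
| ≤5 | passed | positive | not positive | positive |
| ≥6 | failed | positive | not positive | negative |
| ≥6 | passed | negative | not positive | negative |
| ≤5 | not drawn | positive | not positive | positive |

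The arms differ on the two discordant patterns and on MIS-T ≤5 with no clock.

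**Step 2: see whether Step 2: Enrollment settles it.** It does not.

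- For Screen Only it prints *and*, the opposite of Study Design.
- For Screen Plus it has an *or*, a threshold of ≤2 with no test named, and an *and*. This can be read as (MIS-T ≤5) or (≤2 and clock), or as (MIS-T ≤5 or ≤2) and clock.
- On the first of those readings, with 'failed' throughout, MIS-T ≤5 with a passed clock is positive in Screen Plus and not in Screen Only. That reverses the direction in Study Design.
- 'Pass/fail' also appears in the negative rules. Read as 'failed' there, a reassuring letter would require a failed clock, which makes no sense.
- If 'pass/fail' only describes how the clock is scored, the MIS-T cut-off can be read as deciding in both arms, as in Table 2. The clock then has no stated effect.

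**Step 3: illustrate the possible size.** Let a = P(MIS-T ≤5), b = P(clock failed), φ = their correlation and f = the share of patients with both tests. All four are assumed, because the documents give none of them.

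- P(and) = ab + φ√[a(1−a)b(1−b)]
- P(or) = a + b − P(and)
- Discordant patients per arm = 600 × f × [P(or) − P(and)]

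At f = 1:

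| a, b | φ | P(and) | P(or) | Difference | Per 600 |
|---|---|---|---|---|---|
| 0.10, 0.10 | 0.5 | 0.055 | 0.145 | 0.090 | 54 |
| 0.10, 0.10 | 0.3 | 0.037 | 0.163 | 0.126 | 76 |
| 0.10, 0.20 | 0.5 | 0.080 | 0.220 | 0.140 | 84 |
| 0.10, 0.20 | 0.3 | 0.056 | 0.244 | 0.188 | 113 |
| 0.20, 0.20 | 0.5 | 0.120 | 0.280 | 0.160 | 96 |
| 0.20, 0.20 | 0.3 | 0.088 | 0.312 | 0.224 | 134 |

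The range is 54–134 at f = 1, 27–67 at f = 0.5 and 14–34 at f = 0.25. A wider set (a 5–20%, b 10–30%, φ 0–0.3, f = 1) gives 60–228. On the literal reading, the discordant count is also the expected excess of positive disclosures in Screen Only among patients with both tests. MIS-T patients with no clock would add to it at rate a, that is 10–20 per 100 such patients in an arm if a is 10–20%. If the MIS-T alone decided in both arms, the excess is zero.

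**The case against.** The strongest reply is that this is untidy wording around one shared procedure. Background and Study Aims describes screening once for both arms. Table 2 has a single MIS-T cut-off. The Study Design rules are marked as examples. The Screen Plus paragraph in Step 2 refers back to the procedure described for Screen Only. 'Pass/fail' most naturally names a scoring format, and on that reading neither connector imposes a clock condition. The connectors also swap between sections, which is what loose drafting looks like. A literal *and* would leave a Screen Plus patient who could not draw a clock unable to screen positive, against Table 2.

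Most of this stands. A reader might infer that the trial set, or actually used, a stricter threshold in Screen Plus, or that Aim 4 is biased in a known direction. The documents support neither. The arm difference depends on reading 'pass/fail' as 'failed', Step 2 does not repeat its direction, and nothing shows how staff scored patients. Nor can the counts above be turned into a shift in 24-month SF-36, PHQ-9 or GAD-7.

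The reply does not supply the missing rule. An example needs a governing rule elsewhere, and there is none for the MIS-T with a clock. The Mini-Cog rule cannot be borrowed, because it depends on a recall score from a different test. If the MIS-T alone decides, the plan should say so, because it adds the clock expressly to capture what the MIS-T does not.

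**Conclusion.** The rule that triggers the intervention is internally contradictory for patients given the MIS-T with a clock draw, and it cannot be applied uniformly as written. The likeliest cause is a drafting error. Unequal classification by arm is possible but not shown. It would require staff to have followed Study Design literally, with 'pass/fail' taken as 'failed'. In that case Aim 4 would be confounded with unequal disclosure.

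The size cannot be taken from the documents. It runs from zero, if the MIS-T alone was used in both arms, to the illustrative counts above, all of which rest on assumed failure rates, correlation and share tested with both. Patients screened in person with the Mini-Cog have their own rule in Table 2. The point is worth correcting because the rule decides who receives the intervention and the correction is cheap.

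**What to change.** State one identical rule for both arms in Study Design and in Step 2: Enrollment. Write 'failed clock' or 'passed clock' in full, name the test to which the ≤2 belongs, and say that the MIS-T cut-off alone decides when no clock is drawn. In-person patients follow the Table 2 Mini-Cog rule.

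- **Default:** MIS-T ≤5 alone is positive; the clock is recorded but not used to classify. Table 2 stays as it is.
- **Alternative, if the sponsor intended it:** MIS-T ≤5 or failed clock is positive. This flags more patients and needs Table 2 amended to match.

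An *and* rule is the poorer choice. It contradicts the Table 2 cut-off, and it would let the clock only remove positives, although it was added to detect what the MIS-T misses.

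For dyads already screened, cross-tabulate MIS-T by clock (failed, passed, not drawn) by disclosed result within each arm. If the same score pattern was always classified the same way, report that and stop. Only if it was classified differently by arm, add an Aim 4 sensitivity analysis that excludes the affected patterns from both arms: discordant results, and MIS-T ≤5 with no clock if that was affected. The scores precede disclosure, so removing the same patterns from each arm keeps the comparison like with like.

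The cost is a wording amendment, one scoring sheet for both arms and a table from existing baseline data, plus a Table 2 edit under the alternative. No new patients or visits are needed.

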The Control group patients will not be screened at baseline therefore patients and family members will not receive a letter or infographic. Control group patients will be observed through surveillance of their EHR for any screening or incident AD diagnoses that occur as part of routine care for 24 months. At the last follow-up assessment (24 months), we will screen patients in the control group and conduct an interview with the family member to detect possible cognitive impairment.

Specific Aim 1: Evaluate the impact of AD screening on family members' quality of life.

Hypothesis 1: In comparison to the control group, family members randomized to the Screen Only or the Screen Plus groups will express higher levels of health-related quality of life at 24 months as measured by the Short Form Health Survey (SF-36).

Specific Aim 2: Evaluate the impact of AD screening on family members' mood and anxiety.

Hypothesis 2: In comparison to the control group, family members randomized to the Screen Only or the Screen Plus groups will express lower rates of depressive symptoms and anxiety at 24 months as measured by the Patient Health Questionnaire (PHQ-9) and the Generalized Anxiety Disorder Scale (GAD-7).

Specific Aim 3: Assess the impact of AD screening on family members' caregiving preparedness and caregiving self-efficacy.

Hypothesis 3: In comparison to the control group, family members randomized to the Screen Only or the Screen Plus group, will be more prepared for caregiving and have higher self-efficacy at 24 months as measured by the Preparedness for Caregiving Scale and the Revised Scale for Caregiving Self-Efficacy.

Specific Aim 4: Compare the effectiveness of two strategies for diagnostic evaluation and management after AD screening.

Hypothesis 4: In comparison to the Screen Only group, family members randomized to the Screen Plus group will express higher levels of health-related quality of life, caregiver preparedness and caregiving self-efficacy and lower levels of depressive and anxiety symptoms

at 24 months, as measured by the SF-36, Preparedness for Caregiving Scale, the Revised Scale for Caregiving Self-Efficacy, PHQ-9, and GAD-7, respectively.

METHODS

Study Design

- Three arm, blinded, randomized controlled trial
- 1,900 patient-family member dyads from primary care clinics in central Indiana (n=3800)
- 1800 completed baselines; 600 dyads randomized to each of the three study arms

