- Have no prevalent diagnosis of Alzheimer's disease or related dementia and not previously screened for AD as part of a research study.
- Family members will be 21 years or older and identified by the patient as the person who would most likely assist with activities of daily living and/or medical decision making if the patient needed assistance.
- See Table 1 for patient and caregiver inclusion and exclusion criteria

Table 1. Inclusion and exclusion criteria for the proposed trial

Inclusion Criteria	
Patients	Family Members
65 years or older	21 years of older
At least one visit to primary care practice within past 24 months	Lives with the patient or lives within a 50 mile radius
Ability to provide informed consent	Ability to provide informed consent
Ability to communicate in English	Ability to communicate in English
	Identified by patient as the person most likely to provide them care if needed
Exclusion Criteria	
Patients	Family Members
Has a diagnosis of AD as determined by ICD-10 code	Is a non-family member who is not a legal Healthcare Power of Attorney
Evidence of a prescription for a cholinesterase inhibitors or memantine	
Has a serious mental illness such as bipolar or schizophrenia as determined by ICD-10 code	Has a serious mental illness such as bipolar or schizophrenia as determined by ICD-10 code
Permanent resident of a nursing facility	Has a diagnosis of AD as determined by ICD-10 code
Is already enrolled in HABC programs	

Recruitment Sites (as of 9/17/18):

- Indiana University Health Primary Care Practices
- Eskenazi Health Primary Care Practices

Primary outcome: Family member quality of life at 24 months.

Co-Primary outcomes: Family member depressive symptoms and family member anxiety at 24 months.

Co-Secondary outcomes: Family member caregiving preparedness and caregiving self-efficacy at 24 months.

Exploratory outcome: Comparison of all outcomes (noted above) between the family members in Screen Only vs. Screen Plus groups.

Table 2. Measures

Outcomes	Construct/Core Attributes	Outcome measure(s)	Name of Measure	Description	Scoring	When	Source
Primary outcome	Family member Quality of Life	Quality of Life	Medical Outcomes Study Short Form Health Survey 36 (SF-36)	36-items that measure health-related quality of life, mental, physical, and social functioning	Scores range 0-100; Higher scores more QOL	Baseline 6 mos. 12 mos. 18 mos. 24 mos.	Family reported Patient reported

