- **Multi-level mixed effects models** will be used to examine differences in SF-36 scores for both patients and family members using dyadic analytic approaches. For this aim, we will compare family members in the two screening groups (Screen Only and Screen Plus) to those in the no screening (Control) group. Repeated SF-36 scores from both patients and family members will be included as the outcome variables with participant type (patient or family member), group (Screening Only and Screening Plus versus Control), time, and interaction between groups and time as independent variables. We will use a multi-level variance-covariance matrix in the mixed effects models to account for two sources of potential correlations. Correlations from measures obtained from the same individual over time, an autoregressive correlation will be used. Correlations within a dyad between a patient and his/her family member. A compound symmetry structure will be used for the within-dyad correlation. Parameter estimation and hypothesis tests for the mixed-effects models will be conducted using the maximum likelihood approach that provides robust estimation under the missing at random mechanisms.
- A significant interaction between group and time would indicate differences in changes of SF-36 over time between the two screening groups compared to the no screening group. Absence of significant interactions, significant main group effects will suggest differences in SF-36 between groups' at all follow-up times. For Hypothesis 1 we will use a linear contrast for SF-36 from family members in the combined screening groups (Screen Only and Screen Plus) versus the no screening (Control) group at 24 months. We will also include additional covariates in the mixed effects models to determine whether family member characteristics (relationship to patient, frequency or types of contact, etc.) and knowledge of screening are associated with the outcome measures.

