- The multi-level mixed effects models provide a powerful modeling framework for analyzing dyadic outcomes. An alternative model using family member outcomes as the dependent variable and patient outcomes as an independent variable would underestimate variances in outcome measures by ignoring the randomness in the patients' outcomes by treating patient outcomes as fixed covariates. In our proposed models, correlations between patients and their family members on outcome measures (congruence) are explicitly included in the mixed effects models and estimated using maximum likelihood approach. The inclusion of the additional covariance structure due to repeated measures and within dyad correlation also makes it possible to estimate potential differences in patient-family member congruence over time. Comparisons on patient-family member congruence among the groups will be conducted using the likelihood ratio test (LRT) derived from a mixed effects model using group specific correlation structure versus a model using the same correlation in all groups. Changes in congruence can also be conducted using LRT comparing a mixed effects model with time specific correlation structure versus a model using equal correlations across time. By re-aligning data from the family member at specific lag time behind measures from patients, we will also be able to detect a lag effect in family member outcomes using this modeling framework.

Secondary Aim

- **Separate mixed effects models** with PHQ-9 or GAD-7 scores collected at baseline, 6, 12, 18 and 24 months from both patients and family members will be used as the outcome variables for Specific Aim 2. Participant type, randomized group (Screen Only and Screen Plus versus no screening), time and interaction between group and time will be used as independent variables, similarly to the modeling procedures described in details for Aim 1 above. Linear contrasts will be used to compare PHQ-9 and GAD-7 scores from family members in the combined screening groups versus the no screening group at 24 months. Dyad congruence in PHQ-9 and GAD-9 will be examined using LRT from the mixed effects models following the procedure described for Aim 1.

Secondary Aim

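### The Aim 1 and Aim 2 models as listed give one 24-month group difference shared by patients and family members, so the promised family-member contrast cannot be read from them; PHQ-9 and GAD-7 also carry two conflicting outcome labels.

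*Combined protocol and SAP*

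**What the plan says.** **Hypotheses and contrasts.** Hypothesis 1 (Specific Aim 1) predicts that family members in the screening groups will have "higher levels of health-related quality of life at 24 months". The Statistical Plan, Primary Aim, says: "For Hypothesis 1 we will use a linear contrast for SF-36 from family members in the combined screening groups", compared with control at 24 months. The Aim 2 paragraph (first Secondary Aim) does the same: "Linear contrasts will be used to compare PHQ-9 and GAD-7 scores from family members in the combined screening groups".

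**Models.** In both aims the outcome vector holds repeated scores from patients and family members together. The Aim 1 terms are "participant type (patient or family member), group (Screening Only and Screening Plus versus Control), time, and interaction between groups and time". The Aim 2 terms are "Participant type, randomized group (Screen Only and Screen Plus versus no screening), time and interaction between group and time". The covariates that may be added under Aim 1 are family-member characteristics and knowledge of screening. The group-specific structures described for congruence concern correlations, not means.

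**Outcome status.** The outcome list after Table 1 names family-member quality of life as the primary outcome and then adds: "Co-Primary outcomes: Family member depressive symptoms and family member anxiety at 24 months". Table 2 places the PHQ-9 and GAD-7 rows under "Secondary outcomes". No alpha, sidedness, multiplicity procedure or success rule appears anywhere.

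**Power.** The Statistical Power section gives 82.6% for a group-by-time interaction at 0.24 SD with 540 complete dyads per group.

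**The concern.** A model with participant type only as a main effect lets patients and family members differ by a constant, but forces the group difference at each visit to be the same for both. A contrast requested for family members then returns the shared value. Two errors become possible. A real family-member effect can be diluted by patients who do not change, and a change confined to patients can be reported as a benefit or harm to family members, which is the question the trial exists to answer.

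The conflicting labels raise a different problem. Readers cannot tell whether a PHQ-9 or GAD-7 result could by itself make the trial positive, or at what level it would be tested. Finally, the power statement describes a test other than the one named for Hypothesis 1.

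**Working it through.** **Inputs from the protocol.** 1:1:1 allocation; 540 complete dyads per group, so 1080 combined screening against 540 control; effect 0.24 SD (Aims 1-3) or 0.28 SD (Aim 4); linear exponent autoregressive correlation with base 0.2 and decay 0.8; five visits.

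**Assumed.** Two-sided alpha 0.05; equal SDs in patients and family members; categorical time; within-dyad correlation ρ of 0, 0.3 or 0.5, multiplying the over-time correlation; outcome correlations from 0 to 0.9.

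**1. Reproduce the stated power.**
- Correlation at lag d is 0.2^(1 + 0.8(d − 1)/3), which gives 0.200, 0.130, 0.085 and 0.055 at lags 1 to 4.
- Take one series per dyad, a difference growing linearly from 0 to 0.24 SD, and the 4-df group-by-time F test. The noncentrality is (1080 × 540/1620) × 0.03529 = 360 × 0.03529 = 12.71. Power is 82.61% (stated: 82.6%).
- Aim 4, 540 against 540 at 0.28 SD: 270 × 0.04804 = 12.97. Power is 83.42% (stated: 83.4%).

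The stated figures are therefore those of the 4-df interaction test.

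**2. The 24-month family-member contrast.**
- SE = √(1/1080 + 1/540) = 0.0527 SD, and 0.24/0.0527 = 4.55.
- Power = Φ(4.55 − 1.96) = 99.5% at 0.05.
- Power = Φ(4.55 − 2.39) = 98.5% at 0.05/3.

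**3. The contrast under the listed terms.** Under these assumptions, generalised least squares makes the 24-month estimate the mean of the two members' group differences, with SE = 0.0527 × √((1 + ρ)/2). With 0.24 SD in one member and 0 in the other, the expected estimate is (0.24 + 0)/2 = 0.12 SD.

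| ρ | SE | 0.12/SE | Chance of significance |
|---|---|---|---|
| 0 | 0.0373 | 3.22 | 89.6% |
| 0.3 | 0.0425 | 2.82 | 80.6% |
| 0.5 | 0.0456 | 2.63 | 74.8% |

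The table is the same whichever member carries the effect. A simulation of 20,000 trials at ρ = 0.3 gave 80.3% (family-only effect), 80.6% (patient-only effect) and 5.2% (no effect). If both members change by 0.24 SD, the estimate is 0.24 SD and there is no bias. With participant-type-by-group-by-time terms added, the family-member SE is 0.0527 at every ρ tried (0 to 0.7).

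**4. Outcome status.** The chance of at least one false positive among three tests at 0.05 is 1 − 0.95³ = 14.3% at outcome correlation 0. Allowing for correlation, it is 13.6, 12.5, 10.9, 9.8 and 8.4% at 0.3, 0.5, 0.7, 0.8 and 0.9. If SF-36 is the sole primary it is 5%. If all three must succeed, it runs from 0.01% (correlation 0) to 2.3% (0.9).

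**The case against.** **The intent is clear, and a programmer would add the terms.** The Primary Aim paragraph sets out to compare family members, the contrasts name them, and the stated power reproduces with one series per dyad. It would be wrong to infer that the sponsor chose a pooled test; this is an incomplete specification. But the listed terms cannot produce the contrast the text asks for, and nothing in the plan supplies the missing ones.

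**The figures are extreme cases.** This stands. If patients show half the family-member effect, the estimate is (0.24 + 0.12)/2 = 0.18 SD and power is 97.6 to 99.8%, so bias remains but little power is lost. The coding of time is also not fixed, and the power section mentions a continuous time response. With linear time and no patient effect the estimate is still 0.12 SD, but power is about 87 to 97%.

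**The label conflict may be harmless.** SF-36 is the single primary outcome in both the outcome list and Table 2. A reader might infer that the trial runs an 8 to 14% false-positive risk. That requires a rule that any one of three outcomes suffices, which the protocol never states. A reader might also count the Secondary Aim heading over the Aim 2 analysis as a further conflicting label. It is weak evidence, because the same heading covers Aim 4, which the outcome list calls exploratory. The direct conflict between the outcome list and Table 2 remains, as does the absence of an alpha and a success rule.

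**The power mismatch has no consequence for size.** Agreed. The interaction is a planned test, and the contrast has more power than it does. A reader who inferred an underpowered trial would be mistaken.

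**Conclusion.** The main point holds for SF-36, PHQ-9 and GAD-7: the Aim 1 and Aim 2 models as listed cannot separate a family-member group difference from a patient one. Aims 3 and 4 are not affected, because their models use family-member scores. At worst the estimate is halved (0.12 for 0.24 SD) and power drops from 99.5% to 75-90%, with the same 75-90% chance of attributing a patient-only effect to family members. These figures rest on the assumed alpha, equal SDs, categorical time and ρ between 0 and 0.5. The bias shrinks as the two members' effects converge and is zero when they are equal.

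The second point also holds: PHQ-9 and GAD-7 have two incompatible statuses and no stated alpha or success rule. What this costs in false-positive risk depends on a rule yet to be written.

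The power statement needs only a note. It is correct for the interaction but does not describe the test of Hypothesis 1. All of this should be fixed before analysis; none of it calls the sample size into question.

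**What to change.** 1. **Aim 1 and Aim 2 models.** Add participant-type-by-group-by-time terms with their lower-order terms and take the 24-month contrast at the family-member level, or fit family members alone for the hypothesis test. The joint model can be kept for congruence.
2. **Status.** Give PHQ-9 and GAD-7 one label in the outcome list and Table 2, and state two-sided alpha 0.05. If they are co-primary, say whether one or all must succeed. If any one suffices, test SF-36 first or use Holm over the three.
3. **Power.** Keep the 82.6% labelled as the group-by-time interaction, and add the 24-month family-member contrast: about 99.5% at 0.24 SD with 1080 against 540, and about 98.5% at 0.05/3.

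**Cost.** Wording only; recruitment and data collection do not change. The smaller SE from pooling is given up (0.0373 to 0.0456 against 0.0527 SD), but as an estimate for family members it is valid only if both members respond alike, and family-member power is 99.5% without it. If any one outcome suffices, the multiplicity rule makes the threshold somewhat stricter for PHQ-9 and GAD-7, and under Holm for SF-36 too.
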